We will use a Bayesian adaptive algorithm (Berry, 1994) to randomize patients between the two treatment arms. The first 20 patients will be randomized fairly (i.e. fixed allocation of 1:1) between the two arms, after which the response adaptive randomization will begin. As the trial progresses and data accrue, the randomization will become unbalanced in favor of the treatment that, on average, has better results in terms of response, so that each successive patient is more likely to receive the treatment showing better results.

The randomization algorithm based upon this method will be implemented by using the Clinical Trial Conduct website developed by the Department of Biostatistics at M.D. Anderson Cancer Center.

The target enrollment for the study is a maximum of 64 patients, and we expect to enroll an average of 2 patients per month. We will follow all patients until they go off study. We assume a Beta(0.4, 1.6) prior distribution for the probability of response in each arm. We use the following notation: We denote the response rate in the placebo arm as R_p , and the response rate in the eltrombopag arm as R_E . We then denote P_p as the probability that the response rate in the placebo arm is greater than the response rate in the eltrombopag arm. Formally,

$$P_p = \text{Prob}(R_p > R_E \mid \text{data from patients evaluated at day 57}) \text{ and} \\ P_E = 1 - P_p = \text{Prob}(R_E > R_p \mid \text{data from patients evaluated at day 57})$$

The trial will be stopped early and eltrombopag (placebo) selected as being superior if at any time during the course of the trial $P_p > 0.98$ (< 0.02). If the trial is not stopped early and all 64 patients are enrolled and evaluated at day 57, then eltrombopag will be declared superior (inferior) if $P_p > 0.975$ (< 0.025).

After the first 20 patients are randomized fairly, patients will be randomized to the eltrombopag arm with probability $\max(0.20, P_p)$ and to the placebo arm with probability $\max(0.20, P_e)$. In other words, randomization probabilities are subject to the constraint that the minimum randomization probability to either arm is 20%.

The primary endpoint is development of a platelet count $\geq 30 \times 10^9/l$ at day 57 without platelet transfusion within 7 days. Patients who drop out of the trial before completion of day 57 with a platelet count $\geq 30 \times 10^9/l$ at the time of discontinuation will be considered successes with respect to the primary endpoint.

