Patients who drop out of the study after being randomized but before receiving any study drug will not be included in the analysis and will be replaced. All patients who receive a single dose of study drug will be included in the analysis.

Safety Monitoring

Patient safety will be monitored during this trial by reviewing the rate of development of toxicity, relapse, and mortality.

If a patient develops a grade 3 or higher toxicity attributed to the drug, the study drug will be stopped in that patient. This may be recommenced at the discretion of PI after resolution of the toxicity and review of the data.

For grade 4 toxicity, the PI will routinely review patient data and will temporarily halt the study pending study team review if a high rate of unexpected grade 4 toxicity is noticed. The case report form used for data collection will be PDMS/CORE.

We will use a formal Bayesian monitoring rule to monitor the rate of death or relapse on this study. We wish to ensure that the rate of death/relapse at day 57 is no more than 30% in either study arm. If there is a high probability that this rate is greater than 30% in either arm, we will temporarily halt and review the data with the MDACC IRB and FDA before continuing.

The method of Thall, Simon, and Estey will be employed separately in each arm to perform this monitoring. We will assume a noninformative Beta(0.6, 1.4) distribution on the prior probability that a patient experiences death or relapse, which has a mean of 30% but carries little prior information. We will start monitoring with the first patient in each arm and will use the following rule: halt accrual onto an arm if at any time during the course of the study:

$$\Pr\{57\text{-day death/relapse on the arm} > 30\% \mid \text{data from patients evaluable at day 57}\} > 0.925$$

In other words, if at any time during the trial, we determine that there is greater than a 92.5% chance that the 57-day death/relapse in an arm is greater than 30%, we will temporarily halt the arm pending IRB and FDA review.

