This rule leads to the following stopping boundaries: halt the trial if the number of patients that have died/relapsed in an arm out of the number of patients evaluable at day 57 in that arm is $\geq 2/2, 3/3, 4/5, 5/7, 6/8, 7/12, 8/14, 9/17, 10/20, 11/22, 12/25, 13/28, 14/31, 15/33, 16/36, \text{ and } 17/39$. If a decision to stop depends upon data from patients that have been enrolled but who have not yet reached day 57, accrual will temporarily be halted until enough patients are evaluable as to be able to reach this decision. Anticipated study enrollment is 1-2 patients per week, but as an additional safety measure, first 4 patients will be enrolled at a minimum interval of two weeks between consecutive patients.

Joint Operating Characteristics of Adaptive Randomization and Safety Rules
(See table in protocol.)

Analysis Methods
(Details in protocol.)

Where Will Participants Be Enrolled:

Only at MDACC

Is this an NCI-Cancer Therapy Evaluation Protocol (CTEP)? No

Is this an NCI-Division of Cancer Prevention Protocol (DCP)? No

Estimated Accrual:

Total Accrual at MDACC: 64
Estimated monthly accrual at MDACC: 2

Accrual Comments:

Do you expect your target population to include non-english speaking participants? Yes

Please select expected languages of non-English speaking participants. (Select all that apply)
Expected languages of non-English speaking participants:

Spanish

Location of Treatment:

This protocol is performed on an Outpatient basis.

Length of Stay: What is the length & frequency of hospitalization?

N/A

Return Visits: How often must participants come to MDACC?

Every 2 weeks for first eight weeks during the period of active treatment

Home Care: Specify what, if any, treatment may be given at home.

1) Observation without any treatment from week 9 to 12 and 2) Open label phase after week 12 if patient chooses to enrol in it.

Name of Person at MDACC Responsible for Data Management: [[name]](#)

Prior protocol at M. D. Anderson:

Has the Principal Investigator ever had a clinical or behavioral protocol at MDACC that accrued patients?
Yes

Data Monitoring Committee:

Is treatment assignment randomized? Yes

Is this a blinded or double-blinded study? Yes

Does this Protocol need data safety monitoring? Yes

Provide the name of the data safety monitoring board (DSMB) monitoring this protocol:
MDACC DMC

Does this protocol have a schedule for interim and final analysis? Yes

Please describe:
Bayesian adaptive design

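### Safety Monitoring: the printed death/relapse boundary 6/8 does not follow from the 92.5% rule (which gives 6/9), and the text conflicts on whether a crossing halts the arm or the trial

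*Combined protocol and SAP*

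**What the plan says.** All of this is in the Safety Monitoring part of Statistical Considerations.

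- **Prior.** "We will assume a noninformative Beta(0.6, 1.4) distribution on the prior probability that a patient experiences death or relapse", with mean 30%, applied separately in each arm.
- **Rule.** Monitoring starts with the first patient in each arm. The trigger, in words, is "greater than a 92.5% chance that the 57-day death/relapse in an arm is greater than 30" per cent.
- **List.** "This rule leads to the following stopping boundaries": 16 pairs of events over evaluable patients, starting "2/2, 3/3, 4/5, 5/7, 6/8, 7/12, 8/14, 9/17, 10/20" and ending at 17/39.
- **Action, in the rule.** "halt accrual onto an arm if at any time during the course of the study" the criterion is met; restated as "we will temporarily halt the arm pending IRB and FDA review".
- **Action, in the list.** "halt the trial if the number of patients that have died/relapsed in an arm" reaches a listed pair.

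**The concern.** The list is presented as a consequence of the rule, so it can be checked exactly. The entry 6/8 stands out: the gap from 5/7 is a single patient and the gap to 7/12 is four, whereas from 3/3 onward every other gap is two or three.

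This is the plan's only formal boundary for death or relapse, and in practice staff will read the list rather than compute a beta tail area. If the list is more lenient than the rule, an arm that the rule sends for IRB and FDA review carries on accruing.

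The scope of the halt matters for a different reason. In a blinded two-arm trial with adaptive randomization, halting one arm and halting the trial are different actions. If accrual to one arm stops and the other stays open, there is no concurrent randomization during the halt, and the assignment of newly enrolled patients may become apparent. Nor is it clear how a one-arm halt fits the constraint in Adaptive Randomization that "the minimum randomization probability to either arm is 20" per cent.

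**Working it through.** **Inputs** (all from Safety Monitoring): prior Beta(0.6, 1.4); reference rate 0.30; cut-off 0.925; continuous monitoring in each arm.

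**Formula.** With x events among n evaluable patients, the posterior is Beta(0.6 + x, 1.4 + n − x), and the arm halts if Pr(p > 0.30) = 1 − F(0.30; 0.6 + x, 1.4 + n − x) > 0.925, where F is the beta distribution function.

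**Step 1: reproduce the list.** For each n, find the smallest x that triggers, then record the first n at which each x becomes that minimum.

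| Events | 2 | 3 | 4 | 5 | 6 | 7 | 8 | 9 | 10 | 11 | 12 | 13 | 14 | 15 | 16 | 17 |
|---|---|---|---|---|---|---|---|---|---|---|---|---|---|---|---|---|
| Printed n | 2 | 3 | 5 | 7 | **8** | 12 | 14 | 17 | 20 | 22 | 25 | 28 | 31 | 33 | 36 | 39 |
| Rule n | 2 | 3 | 5 | 7 | **9** | 12 | 14 | 17 | 20 | 22 | 25 | 28 | 31 | 33 | 36 | 39 |

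Fifteen of the 16 agree, which also confirms how the list is meant to be read: each count applies from its listed n up to the next listed n.

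**Step 2: the posterior around the failing entry.**

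| x/n | Pr(p > 0.30) | Rule |
|---|---|---|
| 4/7 | 0.9014 | continue |
| 5/7 | 0.9770 | halt |
| 5/8 | 0.9543 | halt |
| 6/8 | 0.9908 | halt, but 5 already suffice |
| 5/9 | 0.9219 | continue |
| 6/9 | 0.9799 | halt |
| 6/11 | 0.9377 | halt |
| 6/12 | 0.9051 | continue |

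Five events are the minimum at n = 7 and 8; six are the minimum at n = 9 to 11.

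**Step 3: can another reading rescue 6/8?**

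- *Another cut-off.* The other 15 entries are all exact only for a cut-off from 0.9248 to 0.9279, which contains 0.925. The entry 6/8 needs 0.9543 to 0.9770, and at that level 2/2 (0.9279) would not be a boundary.
- *Listed n as the last n for each count.* The rule then gives 2, 4, 6, 8, 11, 13, 16, 19, 21, 24, 27, 30, 32, 35, 38, 41, which matches the printed list only at 2/2.
- *A near-fixed comparison standard.* An assumed Beta(300, 700) standard in place of the fixed 30% still gives 5 at n = 8 and 6 at n = 9.

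**Step 4: size.** List and rule differ only at 5/8. Given the earlier boundaries, 14 event sequences reach 5/8 without a prior halt, each with probability p⁵(1 − p)³. At p = 0.30 this is 14 × 0.00243 × 0.343 = 0.0117. Halting probabilities for one arm come from exact recursion. The true rates are assumptions, as the documents give no expected rate.

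| True rate | Reaches 5/8 | Halted by n = 8, list v rule | Halted by n = 32, list v rule |
|---|---|---|---|
| 20% | 0.2% | 5.8% v 6.0% | 6.92% v 7.02% |
| 30% | 1.2% | 14.8% v 15.9% | 25.45% v 25.70% |
| 40% | 3.1% | 28.3% v 31.4% | 61.04% v 61.25% |
| 50% | 5.5% | 45.3% v 50.8% | 90.03% v 90.09% |

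**Step 5: how often the scope question would arise.** With 32 patients in each arm (an equal split of 64) and independent arms, the chance that at least one arm crosses the printed list is 1 − (1 − 0.0692)² = 13% at a true rate of 20% and 1 − (1 − 0.2545)² = 44% at 30%.

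**Step 6: end of the list.** Seventeen events remain the minimum to n = 41 (17/41 gives 0.9322, 17/42 gives 0.9164). The rule then continues 18/42, 19/45, 20/48, 21/51, 22/53. If the first 20 patients split 10 and 10, an arm can hold at most 64 − 10 = 54 patients; 22 events suffice to n = 55.

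**The case against.** The arithmetic is not in dispute. The case on the other side concerns origin, weight and scope.

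*Origin.* The numerical point rests on one digit in a list read from PDF by a program, and an 8 could be a misread 9. That cannot be excluded from the text alone, but nothing in the list itself points to it. It calls for a look at the source page, and the arm/trial conflict does not depend on it.

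*Weight.* The discrepancy lasts for one patient. If the ninth patient has an event, 6/9 halts under list and rule alike; if not, 5/9 no longer triggers the rule. Over a whole arm the difference is at most about a quarter of a percentage point at the rates examined. This stands, and the effect is modest. In the second case, though, the review that the rule required at 5/8 is missed rather than delayed.

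*Scope.* The rule names the arm twice, and either reading stops accrual to the arm that crossed. The text is also an abstract that refers elsewhere to the protocol for the operating characteristics and analysis details, so handling of randomization and blinding may be described there. That limits the claim to the text available. It does not remove the conflict, because the same section gives two different actions for one event.

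*List end.* The rule applies at any time, so nothing beyond n = 41 is unmonitored. This stands: extending the list is optional tidying.

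**Conclusion.** The concern holds on both parts. The entry 6/8 contradicts the rule from which it is said to follow, in the lenient direction; the stated prior and cut-off give 6/9, and with that change all 16 entries agree. The effect on operating characteristics is small: 1.2 percentage points in halting by n = 8 at a true rate of 30%, 5.5 at 50%, and 0.25 over 32 patients at 30%. It still deserves correction, because at 5/8 the list and the rule give opposite instructions on the only formal death/relapse monitor.

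The conflict over halting the arm or the trial has the greater operational consequence and must be reconciled. No view is taken here on which is right.

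The boundary result rests only on the documents' prior, reference rate and cut-off. The probabilities rest on assumed true rates, and the two-arm figures also on 32 patients per arm and independent arms. The point should be fixed; it does not call the design into question.

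**What to change.** 1. Check the fifth entry against the source page. If it reads 6/8, replace it with 6/9, as the stated rule gives.
2. State that each count applies from its listed n up to the next listed n.
3. Reconcile the rule and the sentence introducing the list on whether a crossing halts the arm or the trial, and state what happens to randomization and blinding during the halt.
4. Optionally, extend the list from the same rule with 18/42, 19/45, 20/48, 21/51 and 22/53.

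The cost is one digit, a reconciled statement of the halt, a line on how to read the list and, if wanted, five more entries. The rule, prior, cut-off and sample size are unchanged.
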